- Supplemental routinely collected pseudonymized dental data for all children who were eligible to be seen within a CFDP will be acquired from the dental referral management system and data collected by commissioners and sent to the University of Manchester to be stored in the research data storage. Additionally, identifiable data with assigned ID numbers for these same children will be provided by the dental referral management system to NHS England and NHS BSA following the approval of the Confidentiality Advisory Group (CAG). Pseudo anonymised data provided from NHS England, NHS BSA following linkage with the dental referral management system, will be sent to the University of Manchester Data Safe Haven.
- The Dental Referral Management System will assign unique ID numbers to the pseudonymized data. The RMS system will securely store the identification key, ensuring that only authorized personnel within the system can access it. It will be destroyed as soon as the pseudo anonymised data has been provided to UoM.
- Participants will be shared a copy of their consent via email or via post.
- Audio recordings will be transferred to UoM storage after interviews and deleted from the audio recording device.
- Audio recordings will be kept for as long as the hard copy consent would be.
- Consent will be kept separately to research data

Data will be securely stored securely at the University of Manchester. Where necessary this will be within system compliant for NHS data, all other data will be stored within Isilon storage which is normally used for research data. If NHS/clinical data need to be combined for analysis this will occur within the Data Safe Haven.

All data will be pseudo anonymised. The key will be stored on a separate system from clinical data provided by NHS. With participant consent identifiable information will be provided to third parties such as NHS BSA in order to link the data and for these parties to provide pseudo anonymised back to the study team as part of this research.

Two years after the completion of the study consent forms will be destroyed, the key detailing the connection between identifiable data and ID will be destroyed which will ensure all data is fully anonymised.

IX. Randomization

Not applicable. Prospective, comparative, population based study.

X. DATA ANALYSES

Summary descriptive data will be reported by study arm and overall using tables of frequencies or means and standard deviations as appropriate to characterise the population and identify any imbalance between groups. The comparison of outcomes from the traditional specialist dental service route (control) compared to the intervention treatment under the alternative Child-Friendly Dental Practice will be assessed to determine if there are clinically meaningful and statistically significant differences in key outcomes. The primary outcome is receipt of GA for tooth extraction within two years of initial referral. Referral along both pathways may still result in the need for a GA for some children but a key metric will be to determine whether there

is a meaningful difference in the number of GAs per referral pathway. The primary outcome will be analysed using a mixed effects logistic regression model, accounting for the traditional specialist dental service route or alternative Child-Friendly Dental Practice, with random effects for centre. An adjusted logistic regression analysis additionally accounting for the age, deprivation, ethnicity, sex of the child along with the number of teeth requiring treatment at initial examination (through the CFDP or CDS) will also be undertaken. The analysis dataset will include all participants for whom there is follow-up data from the NHS BSA and the baseline covariates.

Analysis of secondary outcomes will be undertaken in a similar manner using covariate adjusted linear or logistic regression models as appropriate, we will include the modifying effect of deprivation

The health economics analysis will adopt a cost-consequences approach whereby the costs of each pathway will be presented separately but alongside relevant outcomes: 1) dental extractions under GA, 2) count of children who are successfully seen and treated in each pathway, 3) count of treatments performed (extractions, restorations), 4) mean wait time and 5) dental pain experienced by a child. Resource use and costs from the CFDP pathway will also be used in a budget impact analysis. Differences in outcomes will be generated from the quantitative analysis.

The analysis will take an NHS perspective with a 2 year time horizon. Longer term costs and outcomes will not be modelled due to the need for treatment being acute and focusing on child (non-permanent) teeth. This approach will provide dental service commissioners with appropriate health economic data to inform future commissioning decisions related to CFDP. For qualitative data, deductive analysis will be used throughout to complement and enhance other data sources.

Overall the evaluation of Child Friendly Dental Practices will utilise a realist approach (24). This will not only allow the evaluation to determine the impact of the scheme on patients and access to services but will allow us to determine 'what works, for whom, and in what circumstances'. A logic model has been developed based on the initial pilot data, this model will be tested using a mixed methods design using Context Mechanism Outcome configuration. The realist approach therefore will allow us to understand what the linkages are between these different components. The realist approach focuses on the mechanisms which operate in real time along the treatment and referral pathway. The mechanisms reveal the way things really happen, rather than what practitioners, researchers, funders, assume or think happens. Given the complexity of the evaluation and range of perspectives the study aims to capture; a parallel mixed methods study will be undertaken.

XI: Patient and Public Involvement and Engagement (PPI/E)

From a purely practical perspective, ensuring that study recruitment and dissemination activities facilitate the inclusion of diverse groups is essential to ensure the generalisability of the results, ability to capture impacts on social inequalities, and maximise the impact of the research. More universal objectives of patient and public involvement and engagement activities include raising awareness and understanding of the research process, breaking down barriers and increasing trust in science, research, and healthcare, increasing the knowledge of participants about the subject matter, developing a shared understanding of the issues and empowering individuals and communities. These broader underpinning goals are implicit in the patient and public

PANDA study - An evaluation of an alternative Dental Pathway V1.4 02/04/2024 IRAS 323977
involvement and engagement proposals, with more study specific aims and objectives detailed below.

Aim

The aim of the patient and public involvement in this research is to ensure that the study findings will be relevant to the users of this pathway

Objectives

1. To develop communication materials that are clear, understandable, and accessible
2. To design study procedures that promote equality, diversity, and inclusion in research
3. To capture outcomes that reflect the concerns of families going through this pathway
4. To bring patient and public perspectives to the interpretation of the study findings

PPI roles within the study:

PPI lead (DM)

The PPI/E lead is a budgeted member of the research team who has responsibility for the delivery of the study and access to the relevant institutional support, e.g., HR services, budgets, training. The PPI/ E lead will lead the development of the PPI/E strategy, planning and co-ordinating events and activities, recruiting PPI contributors and ensuring adequate training and support, be the main point of contact for PPI/E, will lead the writing up of the impact and outcomes of PPI/E in the study.

Lay co-applicant (EL)

The lay co-applicant is an experienced public contributor who will provide ongoing input into the conduct of the study, design of patient facing materials, interpretation of results and planning of dissemination activities through the quarterly operational management group meetings and associated communications.

In addition, the lay co-applicant may be involved in co-researcher activities. Any involvement will be agreed in advance and will take account of the skills and experience of the lay co-applicant, identified training needs, and areas that they would like to gain further skills and experience in. A University of Manchester honorary contract and training appropriate to any co-researcher activities will be arranged. Example co-researcher activities include:

- a) Assisting with the running of any one-off PPI/E activities
- b) Acting as a mentor / buddy for PPI panel members
- c) Co-chairing PPI panel meetings
- d) Contributing to the evaluation of PPI/E during the study
- e) Contributing to the development of the qualitative interview topic guide
- f) Contributing to the qualitative analysis

PPI panel

We plan to establish a PPI panel which may consist of the PPI co-applicant and three or four other public contributors who have experience of going through the CFDP pathway or the standard paediatric pathway. The PPI panel is intended to open up opportunities for

PANDA study - An evaluation of an alternative Dental Pathway V1.4 02/04/2024 IRAS 323977
involvement in research to relatively inexperienced public contributors, with a view to increasing equality, diversity, and inclusion in research.

The PPI panel will meet around twice a year, or as required, to provide feedback on participant recruitment, patient facing materials, interpretation of study findings, dissemination materials, and dissemination channels. Once recruited, the panel could meet online or respond to requests for feedback via email if appropriate. However, it is recognised that to maximise inclusion, a more flexible approach may be required which may include one-off feedback activities hosted at a dental practice or other suitable venue. The exact format for PPI panel input will be agreed and developed with the panel members.

Funding

PPI contributors will be re-imbursed for their time as NIHR INVOLVE recommended rates.

[NIHR guidance](#) will be followed and contacts for further advice will be shared regarding the potential impact of any remuneration on welfare benefits.

Evaluation

Evaluation of the PPI/E elements within the study will include both and impact evaluation.

Process will be evaluated using an activity-specific evaluation tool, for example, the Public and Patient Engagement Evaluation Tool (PPET V2) developed by McMaster University: <https://ppe.mcmaster.ca/resources/public-and-patient-engagement-evaluation-tool/>

This type of evaluation is useful to capture PPI feedback on specific activities, for example, how well contributors felt they could communicate ideas, if they were listened to, and how easy it was to join the session etc.

Overall outcomes and impact of PPI/E on the study will be evaluated and reporting using the GRIPP2 tool: <https://www.bmj.com/content/bmj/358/bmj.i3453.full.pdf>

XII: Dissemination / knowledge transfer

A full stakeholder engagement plan outlining the range of stakeholders to be engaged with and the most appropriate methods to do so, will be developed iteratively by the Operational Management Groups.

Patient / public focused dissemination:

We will produce plain-language summaries, an infographic and a PPI-inspired animated video. The development of the non-academic dissemination products will be led by the PPI members of the study team. We will seek input and feedback on the products from key stakeholder representatives during their development.

Professional / academic stakeholder focused dissemination:

We will issue press releases coordinated with the CDO's office and the Office for Health Improvement and disparities (OHID) as well as holding webinars for the UK public health community, promoted via links with the Faculty of Public Health and NIHR. We will distribute the briefing materials, infographic and animated video through NHS England regional offices for distribution to their individual dental and medical contract holders via newsletters, meeting notes

PANDA study - An evaluation of an alternative Dental Pathway V1.4 02/04/2024 IRAS 323977
or webpages. We will also share our dissemination products through social media channels that are context-sensitive and relevant for that particular target group, for example, the British Association for the Study of Community Dentistry (BASCD), or the popular members-only Facebook group "For Dentists, By Dentists", which has 14,000 General Dental Council registered members.

The results will be published in a high-impact journal and will be presented nationally for example, at conferences held by the Faculty of Public Health and the British Association for the Study of Community Dentistry,

PEER REVIEW

This research study has been reviewed as part of the funding process from NIHR HSDR

Risks

The burden on participants is incredibly low. They are being asked to consent to the study team to access their records in relation to their dental health/treatment and to complete short text message survey (which they will be compensated for - £10 voucher). The text message survey has been chosen to be easy and quick to respond to.

The potential risk is access to their dental records/data. This will be minimised by keeping the data in the UoM Data Safe Haven, developed to keep NHS data safe and according to NHS data requirements.

STATEMENT OF INDEMNITY

[figure not shown]
The University has insurance available in respect of research involving human subjects that provides cover for legal liabilities arising from its actions or those of its staff or supervised students. The University also has insurance available that provides compensation for non-negligent harm to research subjects occasioned in circumstances that are under the control of the University.

References

1. Levine RS. Childhood caries and hospital admissions in England: a reflection on preventive strategies. *British Dental Journal*. 2021 May 14;230(9):611–6.

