- *What are the health economic impacts of using CFDP?*
 - The study will identify and compare healthcare resource utilisation, and associated costs, of both pathways using data collected from HES, NHS BSA, and local clinical records.

Secondary

- *What are the long-term impacts of treatment in terms of antibiotic use, pain experienced, anxiety, further treatment required by CFDP compared to treatment through a traditional pathway?*
 - Using a text message questionnaire, data will be collected from parents/guardians regarding antibiotic use, pain experienced and anxiety of the patient.
- *What are dental teams' beliefs and views on CFDPs/traditional pathways?*
 - Using a qualitative methodology dental team views will be recorded and analysed.
- *Are patients satisfied with their experience in using CFDPs and traditional services?*
 - Patient experience will be recorded using an adapted version of the NHS Friends and Family Test recorded through a text message questionnaire.
- *Looking only at the CFDPs - what proportion require an onward referral and what characteristics necessitate an onward referral?*
 - The project will assess the characteristics of patients who do and do not require onward referral.
- *Does the scheme work differently across different localities, for different patients?*
 - The project will determine similarities and differences in how CFDP sites operate for the patients they see and treat.

II. INVESTIGATORS

Key Contacts

The Principal Investigator for this study will be:

[name]
University of Manchester
Dental Health Unit
[name]

Other individuals involved in this study include:

[name] [contact]
(University of Manchester; Statistician)

[name] [contact]
(University of Cambridge; Realist evaluation)

[name] [contact]
(University of Manchester)

[name] [contact]
(University of Liverpool; Consultant Dental Public Health)

[name] [contact]
(University of Manchester; Health Economist)

[name]
(Lay co-applicant / PPI advisor)

III. APPROVAL OF THE PROTOCOL

The protocol has been reviewed and approved in writing by NHS ethics (IRAS ID: 323977 REC Reference: 23/EM/0093), and The University of Manchester as sponsor.

The Principal Investigator will ensure all relevant staff participating in the study have appropriate training prior to study commencement.

IV. DURATION OF STUDY

3 Years (see timeline).

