To determine the required sample size, the sample size calculation was based on a two-sample test for proportions. Results indicated that 354 participants per group, 708 participants in total, will allow a difference in proportions in the need for a GA from 25% to 15% to be detected with 90% power and a two-sided significance test at the 0.05 level. We anticipate that at least 10 clinics who are providing care under Child Friendly dental pathway and 10 clinics who are providing care under the usual Specialist Dental pathway will participate in the study.

The study sites are divided into two groups: Community Dental Services (CDS) and Child Friendly Dental Practices (CFDP) with an original planned sample size of 708 participants from both groups, or 354 per group **at the end of the study**. Due to low recruitment numbers from the CFDP group among the study sites, the remainder of the required sample size for the CFDP group will be supplemented with unconsented, **anonymised** data obtained from the dental referral management system, **the data will be from a similar timeframe** of the consented data collected in the CDS group obtained from the study sites.

In 2023, 230 patients were seen and treated within CFDP if the same number are seen and treated within 2024 this will provide data on 460 patients. As we would have a larger sample from the CFDP this would mean only 292 patients would need to be recruited from the CDS to reach a power of 90% to detect a difference in proportions in the need for a GA from 25% to 15%. This approach will allow the study to meet its target sample size and effectively address the research questions and objectives. Recruitment and numbers seen through CFDP will be closely monitored so that recruitment can end as soon as the minimum sample size is reached.

Inclusion / exclusion characteristics

Child aged 4-15 years only (cut-off 16th birthday)

Child resident in Greater Manchester

Child referred by general dental professional based in Greater Manchester

Child contact information complete i.e., age, contact address, telephone number, carer

Extractions requested and radiograph provided

Child medical history complete

Reason why treatment cannot be provided by referring dentist provided

Dental charting complete

Child with no or mild medical complexities

Child with no or mild behavioural complexities

Child presents with symptomatic teeth in one or two quadrants only

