A referring dentist should chart all teeth in a referral indicating all teeth that are carious and which are symptomatic. When deciding triage outcome, if one or two teeth only are symptomatic (i.e., causing pain) and this could be managed by extraction/restoration, then the child would be suitable for management within CFDP. The child should attend the referring dentist for completion of treatment (shared care model).

Not suitable for management in CFDP:

Child who has developmental defects of permanent teeth requiring treatment

Child with three or more symptomatic carious teeth

Child with unrestorable teeth in three or four quadrants e.g., extractions indicated in three or four quadrants

Child who needs root canal treatment (RCT) in permanent teeth

Child with moderate to severe medical complexities

Child with moderate to severe behavioural complexities

VII. STUDY DESIGN Prospective, comparative, observational cohort study

VI: Planned interventions:

The exposed cohort will receive care following triage and treatment through the alternative pathway (treatment through the new CFDP).

The control cohort (non-exposed) will receive care following triage and treatment through the traditional pathway (treatment through the Specialist Paediatric Dental pathway).

Time scale (see appendix for more detailed time line)

Year 1 – 2023

Months Feb-March -Study set up

Months Feb-March -Ethics application

Months March – PPI development,

Months May -December (2024) – Recruitment

Months May - December (2024) – Data collection (CRF)

Months May – September – Observational data collection

Months May – March (2024) -text message survey

Months Nov – Dec – Data coding

Months August to October – Qualitative interviews

Year 2 – 2024

Months Jan -Feb – NHS BSA application

Months May-July – Text message survey

Months May – September – Observational data collection

Months August to October – Qualitative interviews

Months November to December -Qualitative analysis

Year 3 – 2025

Months March – April finalise NHS application

Months May – August -text message survey

Month June – August – NHS data retrieval (NHS BSA, CDS, clinical records, NHS digital, HES)

Month September – November – Data analysis

Month November -Jan – report write up

Year 3 – 2026

Month Jan – March -Dissemination

Outcomes

Proposed outcome measures

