A steering group, will monitor this study at periodic intervals. This group will include the Principal Investigator, University of Manchester staff, lay member of the community (Public and Patient Involvement (PPI) to ensure that the study is being conducted according to Good Clinical Practice Guidelines. An Oversight Committee (chaired by [name]) will monitor and feedback to both the research group and NIHR. Further PPI - patient and public involvement - will be sought for various aspects of the study including visits to practices for recruitment opportunities and through organisations which work with parents and children (such as sure start) to gain relevant opinions on the study, for example both the questionnaire and leaflet will be given to parents to fill in to test before the study begins.

The research will be monitored by the Lead Investigator on a weekly basis and at key project milestones.

The study will be subject to the audit and monitoring regime of the University of Manchester.

VIII. Data handling

The data controller will be the University of Manchester. Data will be collected through

- Clinical examinations. Dentists at the CFDP or CDS will fill out a Case report form (CRF) including information on treatment, antibiotic use (see Appendix B) - pseudo anonymised
- Text message surveys. Participants will answer text message survey at baseline, 1 year and 2 years after consent (See Appendix B). Surveys through text message survey (Text messages will be sent to participants using SafeMessage. SafeMessage is operated by FDS Consultants who are an NHS Business Partner (ODS: 8J025) who have met the following regulatory and legislative requirements: Fully completed NHS

DSPT, CyberEssentials Plus, Data stored in HSCN servers within ISO27001 certified, UK only data centres, DCB0219 met, Clinical Safety Officer, Data Protection Officer and Calidcott Guardian. The system is regularly penetration tested and complies with all the requirements of NHS Digital for the safe storage of sensitive data under GDPR.)

Answers from text message survey will be transferred to csv and pseudo anonymised

- Routinely collected data. Following participants consent, data will be linked and collected to be used within the study. This data will come from but not limited to NHS BSA, NHS England, HES, clinical records from the Community Dental Service, GDP and CFDP and referral forms (See appendix B) this data will be pseudo anonymised.

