Indicate if following is requested (GA)	GA no GA
Previous dental history	free text
Main reason for referral	tick box
Teeth requested for treatment within referral	dental chart
Complexity score	tick box
Reason for referral	free text
Medical behaviour indicators	tick box
Patient anxiety question	5 questions on likert scale
radiograph included	yes no
Date of referral	date

Text message survey

	Text message Question	Potential response
1	Does your child have any pain in his/her mouth/teeth at the moment? Please reply: yes or no.	"Yes" / "No"
1a	If yes, how would he/she rate this pain from 1 (not too painful) to 10 (most painful pain ever)?	"1-10"
2	Has your child received any antibiotics for a dental problem recently for example, in the last year?	"Yes" / "No" / "Can't remember"
2a	If yes, do you remember how many days he/she was given and for how long did he/she take them? Just type your answer below.	Open text
3	In the last 3 months, has your child had any of the following problems: pain, difficult sleeping, problems eating/drinking?	"pain" / "sleeping" / "eating/drinking"
4	Overall, how was your experience of the service you attended for your child's dental treatment. Please reply: very good, good, neither good nor poor, poor, very poor?	"very good" / "good" / "neither" / "poor" / "very poor"
5	Did you feel the service your child attended for their dental treatment was appropriate for your child? Please reply: yes definitely, yes to some extent, no	"yes definitely" / "yes" / "no"
6	Would you recommend the service to family and friends? Please reply: yes, no, not sure	"Yes" / "No" / "Not sure"

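### The listed text survey has no anxiety item, and its two-year wave falls after the last survey window for most consent months

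*Protocol*

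**What the plan says.** Protocol, Research objectives, asks as a secondary question: "What are the long-term impacts of treatment in terms of antibiotic use, pain experienced, anxiety, further treatment required by CFDP", compared with the traditional pathway. The method given beneath it is: "Using a text message questionnaire, data will be collected from parents/guardians regarding antibiotic use, pain experienced and anxiety of the patient".

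Appendix B, Text message survey, lists six numbered questions, two of them with a follow-on:
- Item 1: "Does your child have any pain in his/her mouth/teeth at the moment", with a 1 to 10 rating in 1a.
- Item 2: "Has your child received any antibiotics for a dental problem recently for example, in the last year", with duration in 2a.
- Item 3: "In the last 3 months, has your child had any of the following problems: pain, difficult sleeping, problems eating/drinking".
- Items 4 to 6: experience of the service, its appropriateness, and willingness to recommend it.

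The referral form, also in Appendix B, carries a patient anxiety entry of five Likert questions. The secondary outcomes under Outcomes do not include anxiety.

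On timing, section VIII (Data handling) says: "Participants will answer text message survey at baseline, 1 year and 2 years after consent". Section VI, Time scale, gives recruitment from May 2023 to December 2024 and three survey windows: May 2023 to March 2024, May to July 2024, and, in 2025, May to "August -text message survey". Data analysis follows in September to November 2025.

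**The concern.** There are two separate mismatches. First, an objective names a measure that the instrument does not contain. If the listed survey is what parents receive, the pathways cannot be compared on anxiety after treatment, because the only value comes from before it.

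Second, the survey schedule is set from each family's consent date, but the calendar that has to carry it stops too early for most families. Two-year parent-reported data would then come from the earliest consenters only, who may differ from later ones in site, waiting time and stage of the scheme.

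This affects more than a minor item. Dental pain experienced by the child is a listed secondary outcome. It is also one of the five outcomes set beside costs in the cost-consequences analysis, which has a 2-year horizon. The CDS and CFDP forms and the NHS BSA headings in Appendix B have no dedicated pain field, so pain at follow-up rests essentially on this survey.

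**Working it through.** The plan gives no figure of its own for survey completeness. Its sample size of 354 per group concerns general anaesthetic and does not enter here.

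**Anxiety: the sources side by side**

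| Source (Appendix B) | Anxiety recorded? | When |
|---|---|---|
| Text survey, items 1 to 6 | No | Baseline, 1 year, 2 years |
| CDS and CFDP forms | No | Wait and treatment |
| NHS BSA headings | No | Each course of treatment |
| HES/NHS Digital/CDS headings | No | Follow-up |
| Referral form | Yes, five Likert questions | At referral, before treatment |

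Follow-up anxiety values as listed: none.

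**Timing: inputs**
- Consent months, from Time scale: May 2023 to December 2024, which is 8 + 12 = 20.
- Survey due dates, from Data handling: consent + 0, + 12 and + 24 months.
- Windows, from Time scale: May 2023 to March 2024, May to July 2024, May to August 2025.

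**Two-year wave.** Consent month + 24 must be no later than August 2025, so consent must be no later than August 2023. That leaves May, June, July and August 2023: 4/20 = 20% of consent months, and 16/20 = 80% fall after the last window. A family consenting in December 2024 is due its 2-year text in December 2026. That is 16 months after the last window and later than the January to March 2026 dissemination period.

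**One-year wave.** Consent month + 12 must be no later than August 2025, so consent must be no later than August 2024: 16/20 consent months. Read against the windows themselves, the 12-month date falls inside one only for consent in May to July 2023 (3 months, due May to July 2024) and May to August 2024 (4 months, due May to August 2025): 3 + 4 = 7 of 20.

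**Sensitivity to accrual.** Monthly consent numbers are not given. If the first four months recruited at k times the later rate, the share of consenters able to reach 2 years is 4k/(4k + 16):
- k = 1: 4/20 = 20%
- k = 2: 8/24 = 33%
- k = 3: 12/28 = 43%
- k = 4: 16/32 = 50%

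A steady monthly decline of about 15% would also bring the share to one half.

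**Sensitivity to early closure.** Recruitment may stop once the minimum sample is reached, so 20 months is a maximum. This protocol version is dated April 2024, the 12th recruitment month, and still plans recruitment. Closing at the end of that month would give 4/12 = 33% under uniform accrual.

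**Sensitivity to the survey cut-off.** If texting continued beyond August 2025, the consent months reaching 2 years would be:
- to November 2025 (end of analysis): 7/20 = 35%
- to January 2026: 9/20 = 45%
- to March 2026: 11/20 = 55%

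**The case against.** The strongest reply is that the secondary question survives largely intact. A reader might infer from these mismatches that the survey cannot answer it at all, and the documents do not support that. Pain is in items 1, 1a and 3. Antibiotics are in items 2 and 2a, on the CDS and CFDP forms and in the NHS BSA headings. Further treatment comes from routine records. Only anxiety has no follow-up source. It is also absent from the outcome list and from the long-term outcomes named in the rationale, so this may be a stray word in one objective and not a lost endpoint. That stands, and it is why removing the word is an acceptable fix.

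The survey table may also be incomplete. Outcomes promises questions on adverse experiences and a free-text comment that the table lacks. The Time scale refers to a fuller timeline whose chart is not shown, and the end of study is defined by receipt of NHS data and not by a date. These are fair limits. They do not remove the contradiction in the text as it stands, because analysis is still listed for September to November 2025.

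Two further inferences should be resisted. The 16 of 20 consent months reaching 1 year by August 2025 is not the share that would be surveyed at 1 year: read literally, the windows have gaps and cover only 7. Also, the Sample size section says of the unconsented CFDP records: "This approach will allow the study to meet its target sample size and effectively address the research questions and objectives". A reader might take this as a claim that those children supply survey outcomes. The sentence closes a paragraph on the sample size for the general anaesthetic comparison, and nothing in the Protocol promises survey data from them.

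**Conclusion.** Both mismatches hold on the text shown. As listed, the plan yields no anxiety data after referral. It also yields 2-year survey data from at most 4 of 20 consent months: 20% of consenters under uniform accrual, before non-response. The finding that most consenters miss the 2-year wave rests on an accrual assumption. It fails only if the first four months held at least half of all consenters, or if the survey ran on to about March 2026. The 1-year wave is reachable by August 2025 for 16 of 20 consent months, provided texts are not confined to the listed windows; if they are, for 7.

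The point concerns a secondary objective and the pain outcome in the cost-consequences analysis. The primary outcome and the sample size are unaffected. Pain and antibiotics can be partly answered at baseline and 1 year.

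**What to change.** 1. **Anxiety.** Either add the referral form's five anxiety items to the 1- and 2-year texts, list anxiety as an outcome and analyse it adjusted for the referral score, or remove anxiety from the secondary question and its method. Adding items takes the survey from six numbered questions to eleven and may lower response. The Protocol does not say who answers the referral items, so their comparability with a parent's text reply needs checking first.
2. **Survey dates.** Replace the calendar windows in Time scale with texts sent by consent date, as Data handling already implies, up to a stated data lock. This closes the gaps at 1 year.
3. **Time point and population.** State that 2-year survey results come only from consenters who reach 2 years before data lock, that 1 year is the time point available for most, and that survey outcomes describe the consented cohort only. Carry this through to the pain outcome in the cost-consequences analysis.
4. **Antibiotics.** Do not treat the CDS and CFDP form fields as a substitute for long-term survey data. They match the listed outcome for the wait and treatment period but do not measure use after it.

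The cost is a protocol amendment, a revised survey if anxiety is kept, and a change to the sending schedule. Survey dates that have already passed cannot be recovered.
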